### 8.1.2 Methodology for analysing the main objective

Any AF re-occurrence event (Tables 5, 6 and 7) during the “blanking period” will be not be considered. “Blanking period” starts with the day of the first documented procedure and ends at exact 90 days. The first documented date of AF re-occurrence will be set as the event date. “Blanking period” for patients with additional procedure(s) at any time will not be started newly, they will be considered as “not-event free” at time of the first additional procedure.

Freedom from AF re-occurrence at 12 months will be estimated using Kaplan-Meier methods (time-to-first-event-analysis). A point estimate at the date of 12MFU post first documented procedure will be presented. Standard error will be approximated using

Greenwood's formula, and a two-sided 95% log-log confidence interval will be presented. For patients without a reported AF re-occurrence event, those patients will be censored. In this case, the right-censoring time will be set to the last study contact date. Main objective Kaplan-Meier estimation results will be displayed in percentages at 12 months (351 days) after first documented procedure. Estimated AF re-occurrence rates by month (at the end of month 3 to 11 after first documented-procedure) will be calculated and displayed as well. For group comparisons Log-Rank test will be applied. Also, Hazard ratios and 95% confidence intervals will be shown (for group comparisons, please see SAP chapter 8.6). For Kaplan-Meier estimation, numbers at risk will be displayed for reasonable points in time.

Re-occurrence of AF during 12 months (considering the "blanking period") will also be analysed via Cox proportional hazard regression model presenting hazard ratios and the corresponding 95% CI. Independent variables will be determined by Phased RFA procedure experts or physicians. Cox modelling for AF re-occurrence will be done for all pre-defined subgroups (FAS patients) where the analysis scope is the 12 month outcome (SAP chapter 8.6.1). Further Cox modelling (e.g. for multiple AF events) may be applied.

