## Appendix C: Subgroup analysis

Predefined subgroups (V1.0)

Subgroup description	Analysis set, additional inclusion or exclusion criteria	Tables and scope for analysis
Indication to schedule Phased RFA: Paroxysmal AF	FAS, EFAS incl.: --- excl.: ---	Baseline First documented procedure Additional procedure 12MFU
Indication to schedule Phased RFA: Persistent AF	FAS, EFAS incl.: --- excl.: ---	Baseline First documented procedure Additional procedure 12MFU
Indication to schedule Phased RFA: Longstanding persistent AF	FAS, EFAS incl.: --- excl.: ---	Baseline First documented procedure Additional procedure 12MFU
Successful first documented procedure	FAS, EFAS incl.: --- excl.: ---	Baseline First documented procedure Additional procedure 12MFU
Non-successful first documented procedure	FAS, EFAS incl.: --- excl.: ---	Baseline First documented procedure Additional procedure 12MFU
First documented procedure: PVAC GOLD solely	FAS, EFAS incl.: Phased RFA catheters = PVAC GOLD, general number if catheters used = 1 excl.: adjunctive devices used during the procedure, disregarding sheaths used	First documented procedure Additional procedure GFU 12MFU
First documented procedure: PVAC GOLD + other catheters	FAS, EFAS incl.: Phased RFA catheters = PVAC GOLD, general number if catheters used > 1, additional Phased catheter used (MAAC, MASC and/or Other) excl.: adjunctive devices used during the procedure, disregarding sheaths used	First documented procedure Additional procedure GFU 12MFU
First documented procedure: Phased RFA catheter solely	FAS, EFAS incl.: Phased RFA catheters used, general number if catheters used = 1 excl.: adjunctive devices used during the procedure, disregarding sheaths used	First documented procedure Additional procedure GFU 12MFU
First documented procedure: Phased RFA catheter + adjunctive devices	FAS, EFAS incl.: Phased RFA catheters = PVAC GOLD, general number if catheters used > 1, additional Phased catheter used (MAAC, MASC and/or Other), adjunctive devices used during the procedure excl.: ---	First documented procedure Additional procedure GFU 12MFU
Procedure: Patients with multiple procedures	FAS, EFAS	Baseline First documented procedure Additional procedure

	incl.: patients with > 1 documented procedure excl.: ---	GFU 12MFU

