Baseline:  Patient with AF surgery or ablations in history	FAS, EFAS  incl.: prior AF surgery, status post ablation (endocardial, epicardial, Catheter PV, Phased RF, 3D RF or Other ablation technologies) excl.: ---	Baseline First documented procedure Additional procedure GFU 12MFU
Baseline:  Patient without AF surgery or ablations in history	FAS, EFAS  incl.: no prior AF surgery, no status post ablation (endocardial, epicardial, Catheter PV, Phased RF, 3D RF or Other ablation technologies) excl.: ---	Baseline First documented procedure Additional procedure GFU 12MFU
Baseline:  Reveal implanted patients	FAS, EFAS  incl.: ICM implantation - Reveal XT, Reveal LINQ or other excl.: ---	Baseline First documented procedure Additional procedure GFU 12MFU
First documented procedure:  Anticoagulation in patients with LAAO	FAS, EFAS  incl.: LAAO implantation, anticoagulation medication prior first documented procedure excl.: ---	Baseline First documented procedure 12MFU
First documented procedure:  patients with LAAO	FAS, EFAS  incl.: LAAO implantation excl.: anticoagulation medication prior first documented procedure	Baseline First documented procedure 12MFU
Patients with administrated at least one antiarrhythmic drug (except beta-blocker)	FAS, EFAS  incl.: patients with $\geq 1$ antiarrhythmic medication (except beta-blocker) at any time of this study excl.: ---	Baseline First documented procedure GFU 12MFU
Patients without antiarrhythmic drug therapy	FAS, EFAS  incl.: no antiarrhythmic medication at any time of this study excl.: ---	Baseline First documented procedure GFU 12MFU
First documented procedure:  Patients with discontinued oral anti-coagulation before the procedure	FAS, EFAS  incl.: patients with oral anticoagulation prior to scheduled phased RFA and discontinued before first documented procedure excl.: ---	First documented procedure GFU 12MFU
First documented procedure:  Patients with oral anticoagulation before the procedure	FAS, EFAS  incl.: patients with oral anticoagulation prior to scheduled phased RFA and not discontinued before first documented procedure excl.: ---	First documented procedure GFU 12MFU
Patients lost to 12 month FU	APS, BAS  incl.: patients w/o 12MFU excl.: ---	Baseline First documented procedure Additional procedure GFU 12MFU

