## Appendix D: Analysis of comparison groups

Predefined comparison groups (V1.0)

Comparison description	Analysis set, additional inclusion or exclusion criteria	Tables and scope for analysis	At time of Interim analysis	At time of Final analysis
Age <65, 65-74, ≥75	FAS, EFAS incl.: Age available excl.: ---	Baseline First documented procedure Additional procedure GFU 12MFU	-	X
Body Mass Index <18.5, 18.5 to <25, 25 to <30, ≥30	FAS, EFAS incl.: BMI available excl.: ---	Baseline First documented procedure Additional procedure GFU 12MFU	-	X
EHRA AF symptoms (at admission during the last 12 months) None, Yes – I "No", II "Mild", III "Severe", IV "Disabling"	FAS, EFAS incl.: AF symptoms available excl.: ---	Baseline First documented procedure Additional procedure GFU 12MFU	-	X
Gender Males, Females	BAS, FAS, EFAS incl.: Gender available excl.: ---	Baseline First documented procedure Additional procedure GFU 12MFU	X	X
First documented procedure Regular case, Training case	BAS, FAS, EFAS incl.: Regular or training case available excl.: ---	First documented procedure Additional procedure GFU 12MFU	X	X
Discharge after First documented procedure Patient discharged home, Transferred to another hospital, Death	FAS, EFAS incl.: Discharge available excl.: ---	First documented procedure Additional procedure GFU 12MFU	-	X
Adverse events Patients with AE during 12 months, Patients w/o AE during 12 months	FAS, EFAS incl.: Adjudicated events available excl.: ---	First documented procedure Additional procedure GFU 12MFU	-	X
Re-occurrence of AF Patients with re-occurrence AF, Patients w/o re-occurrence AF during 12 months	FAS, EFAS incl.: --- excl.: ---	Baseline First documented procedure GFU 12MFU	-	X
First documented procedure Phased RFA <40 min of fluoroscopy time vs. ≥ 40 min of fluoroscopy time	BAS, FAS, EFAS incl.: Fluoroscopy time available excl.: ---	First documented procedure Additional procedure GFU 12MFU	X	X
First documented procedure	BAS, FAS, EFAS	First documented procedure Additional procedure GFU 12MFU	X	X

General time of the procedure time <100 min vs. >=100 min	incl.: Total procedure time available excl.: ---			
Patients with more than 5 GFU vs. all other patients	BAS, FAS, EFAS incl.: --- excl.: ---	Baseline GFU 12MFU	-	X
Patients lost to 12MFU vs. not lost to 12MFU (according SAP chapter7)	BAS incl.: --- excl.: ---	Baseline GFU 12MFU	-	X
Analysis of missed data	BAS incl.: --- excl.: ---	Full tables set	-	X

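### Two Appendix C subgroups sent to Cox modelling of AF re-occurrence (antiarrhythmic drug at any time, more than one procedure) are defined by what happens after day 0, so contrasting them gives hazard ratios above 1 even with no true effect

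*SAP*

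**What the plan says.** **The instruction.** SAP 8.1.2 states: "Cox modelling for AF re-occurrence will be done for all pre-defined subgroups (FAS patients) where the analysis scope is the 12 month outcome". It cites 8.6.1, which points to Appendix C. It also says "For group comparisons Log-Rank test will be applied" and "Hazard ratios and 95% confidence intervals will be shown (for group comparisons, please see SAP chapter 8.6", without listing which comparisons are meant. SAP Table 13 sends the Cox results to a forest plot in the FAS and EFAS.

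**The groups.** Three Appendix C rows matter here, each set in the FAS and EFAS with the 12-month follow-up in scope:
- users: patients with one or more "antiarrhythmic medication (except beta-blocker) at any time of this study";
- never-users: "no antiarrhythmic medication at any time of this study";
- "Procedure: Patients with multiple procedures", with "incl.: patients with > 1 documented procedure".

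Appendix D lists "Patients with more than 5 GFU vs. all other patients", and also groups by adverse events during 12 months and by AF re-occurrence itself.

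**The endpoint.** SAP 7.4.1 counts time from the first documented procedure. SAP 8.1.1 applies a 90-day blanking period, evaluates at day 351, excludes patients with a procedure during blanking, and lists pharmacological cardioversion among the events. SAP 8.1.2 treats a patient with an additional procedure as having failed on the date of that procedure.

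For these groups neither document gives a landmark, a time-dependent covariate or a rule fixing status at baseline.

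**The concern.** A Cox covariate that is fixed from day 0 must be known at day 0. These are not.

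- **Drug at any time.** A patient who leaves hospital without a drug, has a recurrence and is then put on one is moved into the user group for the whole follow-up, and that group gains an event. The never group keeps the patients who did not need a drug. The recurrence has determined the exposure.
- **More than one procedure.** Here the fault is circular definition: the act that puts the patient in the group is also the endpoint.

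At stake is how the planned hazard ratios are read. A forest plot could present drug treatment or repeat procedures as risk factors for recurrence when the association comes from the grouping rule. Labelling the analysis exploratory tempers the inference but does not remove the bias.

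**Working it through.** The documents give no hazard ratio, event count or power for these contrasts, so there is no plan figure to reproduce. The inputs below marked as assumed are not in the documents.

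**Step 1. Drug groups, success proportions under a true null.**

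Assumed: recurrence r = 0.30; on a drug at discharge a = 0.40, unrelated to recurrence; a fraction q of the remaining patients start a drug after recurrence; nobody starts one without recurrence.

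- Success in users = a(1 − r) / [a + (1 − a)rq] = 0.28 / (0.40 + 0.18q)
- Success in never-users = (1 − a)(1 − r) / [(1 − a)(1 − rq)] = 0.42 / (0.60 − 0.18q)

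| q | Users | Never-users | False gap |
|---|---|---|---|
| 0 | 0.28/0.400 = 70.0% | 0.42/0.600 = 70.0% | 0 |
| 0.1 | 0.28/0.418 = 67.0% | 0.42/0.582 = 72.2% | 5 points |
| 0.2 | 0.28/0.436 = 64.2% | 0.42/0.564 = 74.5% | 10 points |
| 0.5 | 0.28/0.490 = 57.1% | 0.42/0.510 = 82.4% | 25 points |

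If 5% also start a drug without recurrence, the q = 0.2 case becomes 0.301/0.457 = 65.9% against 0.399/0.543 = 73.5%, a gap of about 8 points. The bias comes from the difference between the two starting rates.

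**Step 2. Drug groups, hazard ratio under a true null.**

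Simulation: 800 patients (the SAP 3.3 figure), constant hazard from day 90 to day 351, complete follow-up, one-covariate Cox model, 300 runs per setting. Assumed: recurrence 20–40%, drug at baseline or discharge 30–50%, 5% starting without recurrence.

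| Start a drug after recurrence | Mean HR, ever vs never | Runs nominally significant |
|---|---|---|
| 5% (same as without recurrence; one setting: 30% recurrence, 30% on a drug) | 0.99 | 4.7% |
| 10% | 1.07–1.14 | 6–20% |
| 30% | 1.49–1.91 | 81–100% |
| 50% | 2.23–3.18 | 100% |

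With the same data grouped by status at baseline or discharge, the mean HR is 0.98–1.01 and 4–8% of runs are significant, about the nominal 5%.

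**Step 3. More than one procedure.**

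Following the rules in order: a procedure up to day 90 removes the patient from the main objective (SAP 8.1.1), and one from day 91 to day 351 is an event on its own date (SAP 8.1.2). Success at day 351 in those FAS patients is therefore 0% by definition. Only patients whose additional procedure falls after day 351 can still count as successes. In one simulated data set (assumed 30% recurrence, half re-ablated), the event rate was 100% in 110 multiple-procedure patients against 14% in the rest, with HR about 17. That number has no clinical meaning. In the EFAS, SAP 4.4 removes patients re-ablated for AF before day 351, so the group is essentially empty up to then.

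**Step 4. More than 5 general follow-ups, if a hazard ratio were produced.**

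SAP 3.1 says general follow-ups may arise from the site schedule, from AF re-occurrence or from adverse events, and gives no frequencies. Assumed: recurrence 20–30%, a mean of 2–3 visits per patient, plus extra visits after recurrence. With no extra visits the HR is 0.91–1.02. One extra visit on average gives 2.3–3.7, and two give 4.1–7.1, again with no true effect.

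**The case against.** **The routing is less definite than it first looks.** The Cox sentence cites 8.6.1 and so covers Appendix C only. A reader might infer that the forest plot will show frequent visits as a risk factor. The documents do not support that: the plot is tied to the Cox regression, and the group with more than 5 follow-ups is in Appendix D. For Appendix D, 8.6.2 names non-parametric tests and odds ratios and speaks of descriptive reports. Hazard ratios reach it only through the general log-rank and hazard-ratio sentences in 8.1.2. This stands. It makes Appendix D a matter of clarification.

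**Cox modelling for subgroups may mean models fitted within each subgroup.** SAP 8.1.2 leaves covariates to experts, 8.6.1 calls the output descriptive, and the multiple-procedure row has no comparator. On that reading no hazard ratio for membership arises from Appendix C. The reading is possible but not stated. Under it, a model within the multiple-procedure group would contain almost only events, so the SAP still needs to say which is meant.

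**The size for drugs is assumed.** This also stands. At a 10% start rate after recurrence the gap is about 5 points and the HR 1.07–1.14. A reader might infer that drugs must appear as a strong risk factor. That does not follow without the actual rate. Use at any time also includes drugs taken from baseline or discharge, so the grouping is only partly post-procedure.

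**Follow-ups are not shown to be often triggered by AF.** SAP 3.1 says only that they might be. More visits also give more chances to detect AF, which is a separate source of bias.

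**Conclusion.** The point holds for the two Appendix C groupings, on condition that they are contrasted. Both use information from after day 0, and nothing in either document corrects for it.

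- **Drug at any time:** with no true effect the hazard ratio is pushed above 1 whenever drugs are started more often after recurrence than without it. The false gap in success is about 5, 10 or 25 points at start rates of 10%, 20% or 50%, given the assumptions in Step 1.
- **More than one procedure:** the contrast is circular in the FAS for procedures from day 91 to day 351, whatever the rates. To call this reverse causation would misname it, and it does not extend to blanking-period procedures or to the EFAS before day 351.
- **Appendix D (more than 5 follow-ups, adverse events, recurrence itself):** 8.1.2 can be read to reach these groups and 8.6.2 points elsewhere, so the sections need reconciling.

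A reader might go further and conclude that the registry's main result is compromised. It is not: the overall 12-month success estimate does not depend on these groupings, and the analyses affected are secondary and exploratory.

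**What to change.** 1. For any Cox, log-rank or hazard-ratio analysis of recurrence, define the antiarrhythmic-drug groups in Appendix C by the discharge medication list. It is already collected (protocol 7.2), tabulated (SAP Appendix B) and used as the pre-value for antiarrhythmic medication (SAP Table 2). The at-any-time rows can remain as descriptive tables.
2. State in SAP 8.1.2 that the multiple-procedure group (Appendix C) and the groups for more than 5 general follow-ups, adverse events and AF re-occurrence (Appendix D) are descriptive only, with no Cox, log-rank or hazard-ratio output for recurrence.
3. Say in 8.1.2 whether Cox modelling for subgroups means contrasts between groups or models within each, and align 8.6.1 and 8.6.2 with that.

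**Cost.** SAP wording only: no new data and no change in sample size. Fewer hazard ratios are reported, and drug starts after discharge no longer affect the grouping. A time-dependent drug covariate would capture those starts, but it needs drug start dates. The documents show medication lists at baseline, discharge and unscheduled visits and no such date field, so that option may not be available at the same cost.

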## Appendix D: Analysis of comparison groups

Predefined comparison groups (V1.0)

Comparison description	Analysis set, additional inclusion or exclusion criteria	Tables and scope for analysis	At time of Interim analysis	At time of Final analysis
Age <65, 65-74, ≥75	FAS, EFAS incl.: Age available excl.: ---	Baseline First documented procedure Additional procedure GFU 12MFU	-	X
Body Mass Index <18.5, 18.5 to <25, 25 to <30, ≥30	FAS, EFAS incl.: BMI available excl.: ---	Baseline First documented procedure Additional procedure GFU 12MFU	-	X
EHRA AF symptoms (at admission during the last 12 months) None, Yes – I "No", II "Mild", III "Severe", IV "Disabling"	FAS, EFAS incl.: AF symptoms available excl.: ---	Baseline First documented procedure Additional procedure GFU 12MFU	-	X
Gender Males, Females	BAS, FAS, EFAS incl.: Gender available excl.: ---	Baseline First documented procedure Additional procedure GFU 12MFU	X	X
First documented procedure Regular case, Training case	BAS, FAS, EFAS incl.: Regular or training case available excl.: ---	First documented procedure Additional procedure GFU 12MFU	X	X
Discharge after First documented procedure Patient discharged home, Transferred to another hospital, Death	FAS, EFAS incl.: Discharge available excl.: ---	First documented procedure Additional procedure GFU 12MFU	-	X
Adverse events Patients with AE during 12 months, Patients w/o AE during 12 months	FAS, EFAS incl.: Adjudicated events available excl.: ---	First documented procedure Additional procedure GFU 12MFU	-	X
Re-occurrence of AF Patients with re-occurrence AF, Patients w/o re-occurrence AF during 12 months	FAS, EFAS incl.: --- excl.: ---	Baseline First documented procedure GFU 12MFU	-	X
First documented procedure Phased RFA <40 min of fluoroscopy time vs. ≥ 40 min of fluoroscopy time	BAS, FAS, EFAS incl.: Fluoroscopy time available excl.: ---	First documented procedure Additional procedure GFU 12MFU	X	X
First documented procedure	BAS, FAS, EFAS	First documented procedure Additional procedure GFU 12MFU	X	X

General time of the procedure time <100 min vs. >=100 min	incl.: Total procedure time available excl.: ---			
Patients with more than 5 GFU vs. all other patients	BAS, FAS, EFAS incl.: --- excl.: ---	Baseline GFU 12MFU	-	X
Patients lost to 12MFU vs. not lost to 12MFU (according SAP chapter7)	BAS incl.: --- excl.: ---	Baseline GFU 12MFU	-	X
Analysis of missed data	BAS incl.: --- excl.: ---	Full tables set	-	X
DAP by country	BAS incl.: --- excl.: ---	Baseline	-	X
Fluoroscopy time by country	BAS incl.: --- excl.: ---	Baseline	-	X

